10.7.1 Intensity of Adverse Events

The severity of the AE will be graded according to the NCI CTCAE Version 4.0 grading scale.² For AEs not covered by NCI CTCAE, the severity will be characterized as mild, moderate, severe, or life threatening according to the following definitions:

- Mild events are usually transient and do not interfere with the patient's daily activities.
- Moderate events introduce a low level of inconvenience or concern to the patient and may interfere with daily activities.
- Severe events interrupt the patient's usual daily activities.
- Life threatening events require urgent intervention to prevent potentially fatal consequences

10.7.2 Relationship of Adverse Events to Investigational Medicinal Products

The causal relationship between the study medication and the AE must be characterized as not related, unlikely, possible/probable, or definitely by the investigator. The following definitions will help guide the cause-and-effect assessment.

Not Related	An AE that, after consideration, is clearly due to extraneous causes (diseases, environment, etc.), which should be specified, if known.
Related	An AE that follows a reasonable temporal relationship to administration of rucaparib. It follows a known response pattern to the suspected drug. It cannot be explained by alternative etiologies It is confirmed with a positive rechallenge or supporting laboratory data.

10.7.3 Outcome and Action Taken

The investigator will record the action taken and outcome for each AE according to the following criteria:

Action Taken with Study Drug

- None
- Dose reduced/delayed
- Rucaparib temporarily interrupted
- Rucaparib permanently discontinued
- Other (specify)

Outcome

- Recovered
- Recovered with sequelae
- Improved
- Ongoing
- Death

- Lost to follow-up

10.8 Follow-Up of Adverse Events, Serious Adverse Events, and Adverse Events of Special Interest

All AEs occurring during the study are to be followed up in accordance with good medical practice until resolved; judged no longer clinically significant; or, if a chronic condition, until fully characterized through 28 days after the last dose of rucaparib. All SAE/AESI should be followed until resolution or stabilization, or until patient is lost to follow-up.

10.9 Regulatory Aspects of Adverse Event Reporting

SAEs, AESIs, and pregnancy must be reported to the Sponsor's SAE designee within 24 hours of knowledge of the event, according to the procedures below. It is important that the investigator provide an assessment of relationship of the SAE to study treatment at the time of the initial report. The Serious Adverse Event/Adverse Event of Special Interest (SAE/AESI) Report Form must be used for reporting SAEs and AESIs, and the Pregnancy Report Form must be used for reporting pregnancies.

Additional information should be reported via facsimile to the number above. Further details on SAE/pregnancy reporting can be found in the investigator's file.

Clovis Oncology, Inc. (Clovis Oncology), or its designee is responsible for submitting reports of AEs associated with the use of the drug that are both serious and unexpected to FDA, according to 21 Code of Federal Regulations (CFR) 312.32, to the European regulatory authorities according to the European Commission Clinical Trials Directive (2001/20/EC); and to other regulatory authorities, according to national law and/or local regulations. All investigators participating in ongoing clinical studies with the study medication will receive copies of these reports for prompt submission to their Institutional Review Board (IRB) or Independent Ethics Committee (IEC). In accordance with the European Commission Clinical Trials Directive (2001/20/EC), Clovis Oncology or its designee will notify the relevant ethics committees in concerned member states of applicable suspected unexpected serious adverse reactions (SUSARs) as individual notifications or through periodic line listings.

Clovis Oncology or its designee will submit all safety updates and periodic reports to the regulatory authorities as required by applicable regulatory requirements.

11 STATISTICAL METHODS

11.1 Analysis Populations

The following analysis populations are defined for the study:

PK-Evaluable Population (Parts 1 and 3 only)—all patients who have received at least one dose of rucaparib and have had adequate PK assessments drawn for determination of the PK profile. Adequacy will be determined on a case-by-case basis and will be assessed prior to analysis of the blood samples.

Food-Effect PK Evaluable Population (Parts 1 and 3 only)—all patients enrolled into a food effect PK evaluation cohort of the study who received rucaparib on both Day 7 and Day 1 (Cycle 1) complied with the fed and fasted requirements, and have sufficient PK data for a comparison to be made between the fasted and fed state.

ECG-Evaluable Population (Part 1 only)—all patients who have received at least one dose of rucaparib and have had adequate PK and ECG assessments performed for determination of the ECG effects in relationship to the PK of rucaparib.

Safety Population—all patients who have received at least one dose of rucaparib.

DLT-Evaluable Population (Part 1 only)—all patients enrolled into Part 1 of the study who received at least 17 complete days of rucaparib and completed Cycle 1 of treatment, or who experienced a DLT in Cycle 1.

Efficacy-Evaluable Population—all patients who met eligibility criteria, received at least one dose of rucaparib, have measurable tumor lesions at baseline, and have at least one post-baseline disease assessment.

11.2 Statistical Methods

11.2.1 General Considerations

The summary tables will be presented for all treated patients by each of the Parts of the study and by appropriate dose groups.

Quantitative variables will be summarized using descriptive statistics (N, mean, standard deviation, median, minimum, and maximum) and/or frequency and percentages for medically relevant categories. Categorical variables will be presented using frequencies and percentages. The Kaplan-Meier methodology will be used to summarize time-to-event variables. If estimable, the 25th, 50th (median), and 75th percentiles will be presented along with the Kaplan-Meier estimates of 3, 6, 9, and 12 month PFS rates. The number of patients with events and the number of censored patients will also be presented.

Individual patient data listings will be provided to support summary tables. All data will be used to their maximum possible extent but without any imputations for missing data.

A statistical analysis plan (SAP) will be available prior to the start of Part 2 of the study. Any deviations from the statistical methods given in the study protocol will be described and justified in the SAP.

All statistical analyses will be conducted with the SAS[®] System.

11.2.2 Patient Disposition

Patient disposition (analysis population allocation, entered, discontinued, along with primary reason for discontinuation) will be summarized using frequency counts, and the corresponding percentages.

11.2.3 Baseline Characteristics

Baseline characteristics and demographic data will be summarized for the safety population.

11.2.4 Efficacy Analyses

The efficacy endpoints in each of the parts of the study will be evaluated using RECIST Version 1.1.

11.2.4.1 Overall Response Rate - Primary Endpoint (Part 2)

A primary efficacy endpoint in Part 2 of the study (ORR) is the best overall response recorded from the start of the treatment until disease progression or recurrence. The ORR will be summarized for the tumor-evaluable population enrolled in Part 2 with frequencies and percentages.

11.2.4.2 Secondary Analyses and Endpoints in Part 2 and 3

11.2.4.2.1 ORR per RECIST v 1.1 and Gynecologic Cancer Intergroup (GCIG) CA-125 Criteria (Part 2)

The proportion of patients with the best response by RECIST v 1.1²⁷ of ‘Complete Response’ or ‘Partial Response’ or response according to the GCIG CA-125^{28,29} criteria will be summarized with number of patients and percent and for each response category.

11.2.4.2.2 Tumor Marker (CA-125) Response Rate Based on GCIG CA-125 Criteria (Part 2)

Only patients with elevated level as baseline will be used for this analysis. The incidence of patients with a response (i.e., at least 50% reduction from baseline which is confirmed at a second post-baseline value) in tumor marker CA-125 will be summarized. The time to CA-125 may also be summarized with Kaplan-Meier methodology where the time to CA-125 is defined as duration between the date of first study drug to the date of the first CA-125 response value (at least 50% reduction). If the patient does not have a response they are censored at the last date of cancer antigen measurement.

11.2.4.2.3 *Progression-free Survival (PFS) (Part 2)*

PFS will be calculated as 1+ the number of days from the date of first dose of study drug to disease progression or death, due to any cause, whichever occurs first. Patients without a documented event of progression will be censored on the date of their last adequate tumor assessment (i.e., radiologic assessment) or date of first dose of study drug if no tumor assessments have been performed. PFS will be summarized using Kaplan-Meier methodology.

11.2.4.2.4 *Duration of Response - Secondary Endpoint (Part 2)*

Duration of response for CR and PR, a secondary endpoint in Part 2, will be measured from the date that any of these best responses is first recorded until the first date that PD is objectively documented. Duration of response will be summarized using descriptive statistics (N, mean, standard deviation, median, minimum, and maximum) as well as categorically.

11.2.4.2.5 *Overall Survival (Part 2B)*

Overall survival is defined as the 1+ the number of days from the date of first dose of study drug to death, due to any cause. Patients without a documented event of death will be censored on the date of their last visit. Overall survival will be summarized using Kaplan-Meier methodology time from randomization until death from any cause, and is measured in the intent-to-treat population.

11.2.4.2.6 *Evaluation of Antitumor Activity – Secondary Endpoint (Parts 1 and 3)*

No formal statistical analysis of efficacy will be performed in Part 1. For patients with measurable disease, response to treatment according to RECIST Version 1.1 will be reported via descriptive statistics by dose level.

11.2.4.2.6.1 *Changes in Tumor Markers Applicable to Patient's Tumor Type (Part 1 and 3)*

Changes in tumor markers applicable to a patient's tumor type will be summarized with summary statistics and may be analyzed in accordance to corresponding tumor marker responder criteria.

11.2.4.3 *Exploratory Endpoints in Part 2*

11.2.4.3.1 *Explore the Association Between Genomic Alterations Identified in Tumor Tissue and Clinical Outcome (Part 2)*

The association between mutational status of BRCA1/2 and other homologous recombination genes, including genomic scarring/LOH assessment in tumor tissue will be evaluated for the response by RECIST v1.1 and/or CA-125. This will be done by evaluating all the efficacy endpoints by mutational status for Part 2.

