
Introduction and Study Overview (cont)	
 Part 3 (Phase II PK portion) = Further evaluation of PK of higher dose strength tablets at the RP2D in patients with any advanced solid tumor, inclusive of lymphoma, with evidence of a BRCA mutation (germline or somatic) 	
Planned Number of Patients	
Number of patients:
 
 Part 1: approximately 50 – 60 patients Part 2: up to 41 evaluable patients in Part 2A and 40 evaluable patients in Part 2B Part 3: approximately 20 evaluable patients 
Patients will enroll in to either Part 1, Part 2, or Part 3 of the study, not in to multiple parts.
	
Planned Number of Sites	
This is a multicenter, multinational study. Patients will be enrolled from approximately 4 – 6 sites in Part 1, approximately 20 sites in Part 2, and approximately 8 sites in Part 3.
	
Study Objectives and Endpoints	
Primary, secondary, and exploratory objectives and endpoints are shown below.
	
	Primary Objectives	Primary Endpoints
	
To evaluate the safety profile of escalating doses of continuous daily oral rucaparib in patients with advanced solid tumors, and to determine the MTD and RP2D (Part 1 only)
	
The incidence of Grade 3 or 4 adverse events (AEs) and clinical laboratory abnormalities defined as dose-limiting toxicities (DLTs)

	
To characterize the pharmacokinetic (PK) profile of oral rucaparib when administered as a continuous daily dose (Part 1 and Part 3 only)
	
PK parameters: area under the curve from time zero to the time with the last measurable concentration (AUC_{0-t}), AUC from time zero to infinity ($AUC_{0-\infty}$), maximum concentration (C_{max}), time to maximum concentration (T_{max}), elimination half-life ($t_{1/2}$), elimination rate constant (k_{el}), apparent volume of distribution at steady state after nonintravenous administration (V_{ss}/F), and apparent total plasma clearance (Cl/F)

To evaluate overall response rate (ORR) in patients with relapsed, high-grade serous or endometrioid epithelial ovarian, fallopian tube, or primary peritoneal cancer associated with a BRCA mutation (Part 2 only) [henceforth abbreviated to ovarian cancer (OC) population]
	
ORR per Response Evaluation Criteria in Solid Tumors (RECIST) Version 1.1; secondary analysis including Gynecologic Cancer InterGroup (GCIg) cancer antigen-125 (CA-125) criteria
	

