5.1.3 Part 2 (Phase II Portion in Patients with BRCA-Mutant Ovarian Cancer)

Enrollment into Part 2 (Phase II portion) will begin when all patients enrolled into the RP2D Expansion cohort have completed two cycles of treatment, or have discontinued from the study prior to completing two cycles of treatment.

Patients enrolled into Part 2 will be assessed for tolerability and efficacy. Patients will be treated until disease progression, unacceptable toxicity, patient or physician request to discontinue, death, or termination of the study.

The Part 2A study will use a Simon 2-stage design to evaluate the efficacy of rucaparib. Initially 21 patients will be treated in Stage 1; if two or more patients in Stage 1 have an objective response (complete response [CR] or partial response [PR]) then the remaining 20 patients will be treated in Stage 2. If fewer than two patients in Stage 1 have an objective response, then no further patients will be enrolled.

The criteria for Stage 1 success were met in April 2014, and Stage 2 enrollment of 41 patients was completed in April 2015.

An additional cohort of 40 *BRCA* mutant OC patients will be evaluated in Part 2B. Enrollment of this portion of the study will begin after enrollment of Part 2A has been completed. Part 2B will run concurrently with Part 3.

5.1.4 Part 3 (Phase II PK Portion in Patients with any Advanced Solid Tumor)

Part 3 will enroll in parallel with Part 2. Part 3 is an initial randomized, single dose, two treatment, two period, crossover design, to explore food effect; with subsequent continuous BID dosing. It is estimated that enrolling approximately 20 evaluable patients will provide sufficient

data for PK analysis. A randomization scheme using blocks of four will assign patients to either a sequence of fasted at Day -7 and fed at Day 1 or a sequence with fed at Day -7 and fasted at Day 1.

After Day 1 patients will continue with BID continuous dosing and will also be assessed for safety and tolerability. Additional detailed PK to assess steady state will be done at Day 15 of Cycle 1. Patients will be treated until disease progression, unacceptable toxicity, patient or physician request to discontinue, death, or termination of the study.

Food-Effect PK Evaluation

All patients enrolled into Part 3 will have plasma samples drawn in order to evaluate the PK profile of a single dose of 600 mg administered as 300 mg tablets in the fed versus fasted state.

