9.10.5.2 Tumor Markers

In Part 1, tumor markers are optional.

In Part 2, CA-125 will be collected at screening, on Day 1 of every cycle, and at the end of treatment visit, performed by a certified local laboratory.

In Part 3 tumor markers appropriate to the tumor type will be collected at screening, on Day 1 of every cycle, and at the end of treatment visit. Appropriate markers are those that are routinely collected to monitor progress of disease eg CA-125 in ovarian cancer; Carcinoembryonic Antigen (CEA) in colon cancer.

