## 4 GENERAL ANALYSIS CONVENTIONS

The summary tables and figures will be presented separately by each study part and cohort (i.e., Part 1, Part 2A, Part 2B and Part 3). There will not be any pooling of data and patients across study parts due to the difference in objectives for each study part. In addition for Part 1, tables and graphs will also be presented by dose groups.

Quantitative variables will typically be summarized using frequencies and percentages for appropriate categorizations and may also be summarized using descriptive statistics. For variables summarized with descriptive statistics, the following will be presented: N, mean, standard deviation, median, minimum and maximum. Categorical variables will be presented using frequencies and percentages.

The Kaplan-Meier methodology will be used to summarize any time to event endpoint. If estimable, the 50th (median) together with a 95% Confidence Interval (CI) together with range will be presented. The number of patients with events and the number of censored patients will also be presented.

Baseline is defined as the last measurement on or prior to the first day of study drug administration.

All data will be used to their maximum possible extent but without any imputations for missing data.

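### If the optional Kaplan-Meier summary of time to CA-125 response is run as written, it can overstate how many patients respond, because non-responders who die or stop treatment are simply censored

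*Protocol*

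**What the plan says.** Protocol 11.2.4.2.2 covers CA-125 response in Part 2. The analysis set is restricted: "Only patients with elevated level as baseline will be used for this analysis". A response is "at least 50% reduction from baseline which is confirmed at a second post-baseline value", and its incidence is the summary that the section commits to. The time analysis is optional: "The time to CA-125 may also be summarized with Kaplan-Meier methodology". It runs from first dose to the first qualifying value, and for everyone else the rule is: "If the patient does not have a response they are censored at the last date of cancer antigen measurement". The reason why measurement stopped plays no part.

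Protocol 9.10.5.2 gives the schedule: "In Part 2, CA-125 will be collected at screening, on Day 1 of every cycle, and at the end of treatment visit". Table 11 shows no CA-125 after that visit, and long-term follow-up for Part 2B (Protocol 9.9) does not include it. Protocol 5.1.3 says when treatment ends: "Patients will be treated until disease progression, unacceptable toxicity, patient or physician request to discontinue, death, or termination of the study". Protocol 7.4.4 lets selected patients continue beyond RECIST progression, with all required assessments.

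The SAP does not list time to CA-125 response in sections 11.2, 11.3 or 12.1 to 12.3. Its general convention (SAP 4) is: "The Kaplan-Meier methodology will be used to summarize any time to event endpoint". SAP 13.1 says that censoring rules stand under each time-to-event endpoint, and none is given for this one.

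**The concern.** Censoring is harmless when censored patients have the same later chance of the event as those still followed. That is reasonable for a non-responder still on rucaparib at data cut-off. It is not reasonable for one who has died, or who has permanently stopped and will give no further CA-125 values. For the question of how many patients respond on treatment, and when, those exits are competing events. Kaplan-Meier redistributes these patients' weight to the patients who remain.

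The risk is in presentation. A reader would take 1-KM as the percentage who have responded by a given time. That figure could be higher than the CA-125 response proportion on the same page, and a median could appear for an outcome that most patients never reach.

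**Working it through.** **Inputs.** From the documents: values every 21 days, none scheduled after end of treatment, and cohort sizes of "up to 41 evaluable patients in Part 2A and 40 evaluable patients in Part 2B" as a ceiling on the analysis set. The documents give no number with elevated baseline, no CA-125-only response rate for Part 2, and no timing of responses or exits. The 47% (RECIST) and 73% (RECIST and CA-125) in Protocol 11.4.2 are not CA-125-only rates. The plan states no figure for this curve, so there is none to reproduce. All rates below are assumptions.

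**Direction.** Let h1 be the chance of response at a visit and h2 the chance of leaving afterwards without response.
- 1-KM(t) = Σ K(k-1)·h1, where K is multiplied by (1-h1) at each visit.
- Cumulative incidence CIF(t) = Σ S(k-1)·h1, where S is multiplied by (1-h1)(1-h2).

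S never exceeds K, so 1-KM is never below CIF. The two are equal if nobody leaves before the last response.

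**Constant hazards.** Let p be the proportion who eventually respond and h the total hazard per month. At 6 months, CIF = p(1-exp(-6h)) and 1-KM = 1-exp(-6ph).

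| h | p = 0.45: 1-KM vs CIF | p = 0.60 | p = 0.75 |
|---|---|---|---|
| 0.25 | 49.1% vs 35.0% (14.1 points) | 59.3% vs 46.6% (12.7) | 67.5% vs 58.3% (9.3) |
| 0.35 | 61.1% vs 39.5% (21.6) | 71.6% vs 52.7% (19.0) | 79.3% vs 65.8% (13.5) |
| 0.50 | 74.1% vs 42.8% (31.3) | 83.5% vs 57.0% (26.5) | 89.5% vs 71.3% (18.2) |

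The excess is 9 to 31 points. With 32 qualifying patients (assumed), the standard error is √(CIF(1-CIF)/32), and the excess is 1.1 to 3.6 standard errors.

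Medians at p = 0.60, h = 0.35: Kaplan-Meier ln2/(0.60×0.35) = 3.3 months; cumulative incidence -ln(1-0.5/0.60)/0.35 = 5.1 months. At p = 0.45, Kaplan-Meier gives ln2/(0.45h), which is 6.2 months at h = 0.25 and 3.1 at h = 0.50, although 55% never respond.

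**Early responses.** A simulation (4,000 replicates, 32 patients, 3-weekly values, non-responders leaving with a median of 4 months) gave 1-KM at 6 months of 50%, 65% and 79% for p = 0.45, 0.60 and 0.75. The true values were 44%, 59% and 74%. The excess is about 6 points, or 0.66 to 0.75 standard errors.

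An expected-value version comes close. Eventual responders respond with probability 0.40 at each of 8 visits, so CIF = p(1-0.6⁸). At visit k the responding fraction is r = p·0.4·0.6^(k-1). The fraction at risk is n = p·0.6^(k-1) + (1-p)·exp(-(ln2/4)·t), with t the previous visit in months (3(k-1)/4.345). Then 1-KM = 1-Π(1-r/n) gives 50.5%, 65.8% and 79.8% against 44.2%, 59.0% and 73.7%. If exits are dated before the next scheduled value (t = 3k/4.345), 1-KM is 53.7%, 68.6% and 81.7%, an excess of 8 to 10 points.

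**Worked 40-patient cases** (visit k is week 3k; no one still on treatment at the end).

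- *16 of 40 respond, exits interleaved.* Responses at visits 1, 2, 3, 4, 6, 8 are 3, 4, 3, 2, 2, 2. Exits at visits 2, 3, 4, 6, 7, 8 are 8, 4, 6, 4, 1, 1. Numbers at risk at the response visits are 40, 37, 25, 18, 10, 3. K = (37/40)(33/37)(22/25)(16/18)(8/10)(1/3) = 0.172, so 1-KM ends at 83% against an actual 16/40 = 40%. Kaplan-Meier prints a median of 24 weeks; the true curve never reaches 50%.
- *24 of 40 respond, all by visit 4, with the first exit at visit 6.* K = (32/40)(24/32)(19/24)(16/19) = 0.40. Both methods give 60% and a median of 9 weeks, so there is no bias.
- *34 of 40 respond.* The curves end at 95% and 85%; both medians are 6 weeks.

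**The case against.** The case against making much of this is strong on status and size.

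- **The analysis is optional.** The committed summary is a plain proportion, which does not have this problem. Time to CA-125 response is in no objectives table, and no sample size, test or decision rule uses it.
- **The SAP may have left it out.** Its one time-to-response endpoint is RECIST-based and reported by week category (SAP 12.3.2). The general Kaplan-Meier convention does not create an endpoint that the SAP omits. SAP 12.1 also refers to an Appendix A on CA-125 response that is not in the text available here, so a rule there cannot be excluded.
- **The bias may be small or nil.** In the early-response simulation it is under one standard error, and in some scenarios the median does not move. The larger figures need response to stay equally likely month after month, which nothing in the documents supports.

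All of this stands and sets the severity. It does not make the rule sound. Protocol 11.2.1 requires deviations from protocol methods to be described in the SAP, and the SAP text describes no withdrawal of this analysis.

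A reader might go further and treat RECIST progression itself as ending the chance of response. SAP Table 2 appears to support this, since it scores RECIST progression with a CA-125 response as no response. That table governs the combined endpoint only. Protocol 11.2.4.2.2 does not limit CA-125 response to the time before progression, and Protocol 7.4.4 allows treatment and assessment to continue after it.

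**Conclusion.** The point holds in a limited form. If the optional analysis is run under the stated rule, 1-KM is at or above the true cumulative proportion responding, never below it. It can disagree with the response rate beside it and can give a median when fewer than half respond. The excess ranges from zero (all responses before all exits), through about 6 points at 6 months with early responses, to roughly 9 to 31 points under constant hazards. These figures assume 45% to 75% eventual response and the exit rates shown; the documents supply neither.

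A reader might infer that the curve and median will certainly be reported and will certainly be too favourable, or that the Part 2 efficacy result is affected. The documents support neither inference. The analysis is permitted rather than planned, non-responders still on treatment at cut-off are properly censored, and the objective response rate does not use this curve. Severity is low.

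**What to change.** Do one of two things in the SAP.

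1. State that the optional time-to-CA-125-response analysis will not be performed. One sentence is enough.
2. If it is kept, replace the censoring rule in Protocol 11.2.4.2.2 and add to the SAP:

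> Time to CA-125 response will be shown as cumulative incidence (Aalen-Johansen), with death or permanent treatment discontinuation without CA-125 response as competing events. Patients still on treatment at data cut-off, including those treated beyond RECIST progression, are censored at their last CA-125 value. Median time to response is given for responders only, next to the response proportion.

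Counting discontinuation for toxicity or by request as a competing event is a choice of estimand: it describes response while on rucaparib. The SAP should say so.

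The first option costs nothing but the sentence. The second needs a paragraph, a little more analysis work and no new data, and it may give a less favourable curve.
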